*Functional Imaging and Neurophysiological Analyses.* Functional images will be analyzed and overlaid onto structural images with the Analysis of Functional Neuroimaging (AFNI) program (Cox, 1996). To minimize the effects of head motion, time series images will be spatially registered in 3-dimensional space. The average functional intensity of each acquired slice for every subject will be normalized to the mean intensity of all slices for all subjects to control for differences in functional intensity between subjects. A subject's data will be excluded from further analyses if any time series of a subject is judged from visual inspection to contain a significant number of images with gross artifacts or residual motion.

*fMRI Analysis.* The current study is concerned with the response of the ipsilateral primary motor cortex during actions performed by right hand. It is hypothesized that sedentary aged adults will initially show an increase in metabolic activity (i.e. – a positive BOLD response) in this area. To assess this, an analysis of average hemodynamic (impulse) response functions in the right primary motor cortex will be performed. These impulse response profiles will be tested across session using repeated measures ANOVA. Significant differences will be assessed at the individual

subject and group level.

For group analysis of intervention effects, anatomic and functional images will be interpolated to volumes with 1 mm^3 voxels, co-registered, and converted to stereotaxic space of Talairach and Tournoux (1988) using AFNI. Estimates of hemodynamic response functions (HRFs) generated from a deconvolution procedure will be spatially smoothed using a 5 mm full-width half-maximum (FWHM) Gaussian filter to compensate for variability in structural and functional anatomy across participants. Area under the curve (AUC) of the HRF's will be entered into a voxel-wise two-way mixed-design ANOVA (age grouping as the between subjects factor, session as the within-subjects factor). Additional pair-wise comparisons of age groupings will be performed using Student's t-test ( $p < .05$ , False Discovery Rate corrected) on a voxel-by-voxel basis with left and right primary motor cortices selected as regions of interest (ROI). Pairwise comparisons will be computed for all motor response conditions.

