*TMS Analysis.* Six measures will be computed and analyzed from TMS acquisitions: Right FDI MEP size, right FDI MEP latency, recruitment curves (RC), ipsilateral silent period (iSP), interhemispheric inhibition at 10ms (IHI10) and 40ms (IHI40). The size of left FDI MEP evoked by TMS will be measured from peak-to-peak between TMS stimulation (first peak) and subsequent muscle response (second peak). The latency of MEPs will be measured from the onset of the stimulus presentation to the onset of the MEP. Recruitment curves will be evaluated based on slope generated from linear regression. Onset and end latency of the iSP will be taken at the initial and final intersections of the averaged signal with baseline indicating 80% of the background EMG level; the duration of EMG suppression between these two points will be computed. For each of the stimulation intensities, IHI will be expressed by  $(1 - \text{mean conditioned MEP} / \text{mean unconditioned MEP}) \times 100\%$ . Accordingly, IHI = 0%, IHI = 100%, and IHI < 0% will indicate no inhibition, complete inhibition, and interhemispheric facilitation, respectively. For within subjects comparison, repeated measures ANOVA with subsequent repeated measures pairwise t-tests will be generated. Group comparisons of TMS measures will be analyzed by between-subjects ANOVA and subsequent t-test pairwise comparisons. For all test, p-values < 0.05, corrected for multiple comparisons where applicable, will be considered statistically significant.

*BDNF Evaluation.* Fasting whole blood will be collected, by a certified phlebotomist, via venipuncture or peripheral venous line into pre-cooled plasma EDTA tubes and serum separator tubes (~40 ml per visit). Following collection, tubes will be transferred in sealed biohazard bags and in according with blood borne pathogens training standards to the Molecular Biology Lab (4A 178/4A 167) of the Atlanta VAMC Center of Excellence.

Plasma volume will be measured using methods described by Dill and Costill. Lactate will be measured by the Accusport Lactate Analyzer (Roche Molecular Biochemicals, Mannheim, Germany). Serum samples will be allowed to clot for 30 minutes before centrifugation at 1000g for 15 minutes. Plasma samples will undergo centrifugation within 30 minutes of collection at 1000g for 15 minutes at 2-8°C. Plasma aliquots will be separated and will then undergo an additional centrifugation "Super-

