**Power Analysis and Sample Size.** We powered this study on the previous cross-sectional studies assessing interhemispheric communication and motor performance. These studies had large effect sizes (1.33 to 1.67) as aerobic activity was related to ipsilateral motor cortical activity. As the proposed work is an intervention, we have applied a conservative estimate of these effects based on previous work with behavioral performance training over a similar timeframe (Kornatz et al., 2005) and those in the neuroimaging literature (Erickson et al., 2011). Further, data from our ongoing CDA-1 pilot study has shown a somewhat linear relationship between VO2max and levels of interhemispheric inhibition. While this data does not provide enough information to enable us to estimate a required sample size under the mixed model that will be used in the final analysis, we can conservatively estimate the sample size assuming a two-sample t-test would be performed on the post-pre differences for each group. Under this simpler model, a sample size of 20 per group will give us an approximate effect size of .83 for the fMRI and TMS measures. While this effect sizes is relatively large, we will have more power under the mixed model that we actually will use to analyze the data. Equally important, from the standpoint of our sample size, is that the data gathered on the other outcome measures would be invaluable in fully powering future study. Lastly, based on the retention rates in previous exercise studies we anticipate a 20 percent

drop-out rate among groups. As such, we will plan to enroll 24 per group to reach the needed sample size of 20 per group.

The research staff will use REDCap issued through the Atlanta Veterans Health Care System. Only deidentified data will be entered into REDCap by VA credentialed research personnel to run data analysis.

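### The stated detectable effect of .83 at 20 per group does not follow from its own t-test basis (0.91 at two-sided 0.05 and 80% power) and makes no allowance for the TMS multiplicity rule

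*Combined protocol and SAP*

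**What the plan says.** Section 7 (Power Analysis and Sample Size) says the available data cannot size the mixed model. It therefore falls back on a simpler calculation, "assuming a two-sample t-test would be performed on the post-pre differences for each group", and concludes that "a sample size of 20 per group will give us an approximate effect size of .83 for the fMRI and TMS measures". No alpha, sidedness, power or adjustment for multiple tests accompanies the figure. The section then says: "While this effect sizes is relatively large, we will have more power under the mixed model that we actually will use to analyze the data". Enrolment is set with drop-out in mind: "we will plan to enroll 24 per group to reach the needed sample size of 20 per group". So 20 is the evaluable number and 24 the enrolled number.

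The rules for judging the same measures are in Section 5, Specific Aim 2. The TMS Analysis paragraph lists six measures and closes with: "For all test, p-values < 0.05, corrected for multiple comparisons where applicable, will be considered statistically significant". The fMRI Analysis paragraph has voxel-wise pairwise t-tests that are "False Discovery Rate corrected) on a voxel-by-voxel basis with left and right primary motor cortices selected as regions of interest (ROI", but attaches that correction to comparisons of age groupings. Section 7 (Aim 2) plans a mixed linear model for each fMRI and TMS outcome, with time, group and their interaction, and mentions no correction.

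**The concern.** The .83 is the only sensitivity figure in the plan. Two things about it look wrong. First, the usual settings for a two-sample t-test do not give .83 at 20 per group. Second, the figure appears to belong to one uncorrected test, while the TMS paragraph calls for corrected p-values where applicable.

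What is at stake is how a null fMRI or TMS result is read. Someone who takes .83 at face value could treat a non-significant result as evidence against an effect of that size. On the t-test basis, the trial would miss such an effect more often than the figure suggests.

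**Working it through.** **Inputs.** From Section 7: two-sample t-test on post-pre differences, 20 evaluable and 24 enrolled per group, effect .83. From Section 5 (TMS Analysis): threshold 0.05 and six measures. Assumed, because not stated for the .83: two-sided testing and 80% power. A one-sided test is also shown.

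**Formula.** With n per group and standardised effect d, the test statistic is noncentral t with 2n − 2 degrees of freedom and noncentrality d × √(n/2). Power is the probability of exceeding the critical value. The detectable effect is the d that gives power 0.80.

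**Step 1: try to reproduce .83.**
- n = 20, two-sided 0.05: noncentrality 0.83 × √10 = 2.62, 38 df, critical value 2.02. Power at .83 is 0.725; detectable effect 0.909.
- n = 24, two-sided 0.05: noncentrality 0.83 × √12 = 2.88, 46 df, critical value 2.01. Power at .83 is 0.804; detectable effect 0.826, which rounds to .83.
- n = 20, one-sided 0.05: power at .83 is 0.825; detectable effect 0.801.
- n = 20, two-sided 0.05, other power levels: detectable effect 0.806 at 70% and 1.052 at 90%.

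The figure is matched at the enrolled number and not at the evaluable number to which Section 7 attaches it.

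**Step 2: illustrate a correction.** Bonferroni, two-sided. The family sizes are assumptions.

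| Tests in family | Alpha | Power at .83, n = 20 | Detectable effect, n = 20 | Detectable effect, n = 24 |
|---|---|---|---|---|
| 1 | 0.05 | 0.725 | 0.91 | 0.83 |
| 2 | 0.025 | 0.62 | 1.01 | 0.92 |
| 6 | 0.05/6 = 0.0083 | 0.45 | 1.15 | 1.04 |

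**Step 3: does the mixed model add power?** Assume five assessments, equal correlation between visits, and a group difference at the first post-training visit only, with .83 scaled to the SD of one post-pre difference. The noncentrality is 1.6 × (20/2) × 0.83² = 11.0, with 4 × 38 = 152 denominator df.
- 4-df group-by-time test: power 0.75 at 0.05 and 0.49 at 0.05/6. The t-test gives 0.73 and 0.45.
- Targeted 1-df contrast with the same noncentrality: 0.91 at 0.05, 0.85 at 0.025, 0.74 at 0.05/6.
- 1-df contrast against the mean of the two pre-intervention visits, noncentrality (20/2) × 0.83² × 2/1.5 = 9.2: 0.85, 0.78 and 0.64.

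As a separate check, suppose the gain is only that of baseline adjustment. The variance relative to a change score is (1 + r)/2, where r is the pre-post correlation. For r from 0.3 to 0.8 (assumed), power at .83 runs from 0.89 down to 0.77 uncorrected, 0.82 to 0.67 for two tests, and 0.68 to 0.50 for six.

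Whether the model gains power therefore depends on the contrast and the correlations, and Section 7 specifies neither.

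**The case against.** The strongest defence is that the multiplicity part depends on things the plan does not say. The TMS correction applies only where applicable, and it follows sentences about pairwise t-tests after ANOVA. It may well mean post-hoc comparisons within a measure and not a family of six measures. The FDR clause concerns age groupings, which this trial of adults aged 60 to 89 does not randomise. The right primary motor cortex analysis in the same paragraph, and the Aim 2 mixed model in Section 7, state no correction. All of this stands, so 1.01 and 1.15 can only be conditional illustrations, and no loss is claimed for voxel-wise fMRI.

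A second defence is that Section 7 may be right about the mixed model. For a targeted contrast under the assumptions above it is: power at .83 exceeds 80% uncorrected and also for two tests. That stands too. But the plan names no such contrast, and the omnibus interaction gains almost nothing. The five-visit calculation also ignores that the groups are split again before the final assessment (Section 5, Specific Aim 3), which is a further reason for the plan to give its own calculation.

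Third, Section 6 allows a larger enrolment of 60 to 80. It still aims for 40 completers, which is 20 per group, so it does not support reading .83 at 24 evaluable per group. Section 7 does call the figure approximate and relatively large, but neither word supplies the missing alpha, sidedness and power.

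A reader might infer that 20 per group cannot detect .83 under the tests the trial will run. The documents do not support that. Even Bonferroni over six measures leaves power at 0.45 on the t-test basis, which is reduced power and not inability.

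**Conclusion.** The point holds in a limited form. On Section 7's own t-test basis, with two-sided 0.05 and 80% power assumed, 20 evaluable per group detect 0.91 and not .83; power at .83 is about 73%. This shortfall exists before any correction. An unstated one-sided 0.05 test would bring the figure close (0.80), so the missing inputs are themselves part of the defect. Any correction across measures can only raise the detectable effect on that basis, but by how much is unknown until the family and method are named.

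It would go too far to present 1.15 as the trial's true detectable effect, or to say that the mixed model cannot make up the difference. The first presumes a six-measure Bonferroni family that is not in the plan. The second holds for the 4-df test but not for a targeted contrast.

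**What to change.** In Section 7 (Power Analysis and Sample Size):
- Replace .83 with 0.91 SD of the post-pre difference at 20 evaluable per group, and state 80% power, two-sided 0.05, no multiplicity correction. If other settings were intended, state those and the figure that follows from them.
- Say whether a correction across measures applies to the group comparisons, and name the family and method. If it applies, quote the detectable effect at that alpha: with Bonferroni, 1.01 for two tests or 1.15 for six. Which measures belong in the family is the sponsor's choice.
- Support the claim of more power under the mixed model with a calculation for a named contrast and stated correlation assumptions, or delete it.

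The cost is some rewording and one short power calculation. Enrolment need not change. The downside is that the stated detectable effect becomes less favourable.

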### **8. Adverse event reporting:**

In the case of a reportable event, the Principal Investigator will complete the form “Reportable Protocol Event Form for VA sites,” attach supporting documentation, and provide it to the VA Science Information Office. The SIO will then route the report to the Emory IRB. The Emory IRB will be notified within five days of any adverse event occurring.

### **9. Data and safety monitoring plan (DSMP)**

This is a minimal risk protocol and therefore data will not be reviewed by a Data Safety Monitoring Board (DSMB) or Data Monitoring Committee (DMC).

This study will only recruit healthy older adults. Prior to beginning any portion of this study we must receive a physician’s written medical approval for participation in physical activity. We will contact the physician and inform him/her of their patient’s interest in participating in this study and explain the study criteria for participation detailing the intervention and testing procedures. Additionally, the pre/post testing carries minimal risks due to the sub-maximal nature of the fitness testing. As per the YMCA protocol, “physician supervision is not necessary with sub-maximal testing in low to moderate risk adults.” (ACSM’s Health Related Physical Assessment Manual, 2007). Although any exercise program carries with some possibility of exercise-induced cardiovascular events, we will minimize this by including those who have been cleared by a health care professional. While the risk of a cardiac emergency is increased when a person is exercising, these events are rare and usually occur during high-intensity activities. This study will utilize a moderately intense exercise regiment for all participants. The cardiovascular benefits of exercise have been consistently shown to outweigh the acute cardiovascular risk during the act of exercising. Moreover, a person beginning a moderately intense exercise program is actually at a lower overall risk of sudden death than their sedentary peer.

### **Protection Against Risk**

Several precautions will be made to reduce the risk of exercise-related injuries:

- The exercises are carefully designed with warm-up, stretching and cooling down components to minimize injuries;
- Written instructions highlighting some fundamental guidelines all study participants should do to ensure that they are exercising safely will be provided to all study participants;
- For those individuals who are extremely de-conditioned, frequent rest periods and exercise from a sitting position will be offered at the beginning of the training period;
- At each exercise session, participants will be questioned about the presence of musculoskeletal symptoms;
- If a participant experiences a significant illness requiring mobility restriction, surgery or hospitalization, the project coordinator will contact the participant's primary physician for clearance to return to the intervention classes.
- If adverse symptoms develop a 1-week hiatus from the exercise session will be enforced, and during this time the participant will perform static stretching exercises. A slow reintroduction of the exercise program will follow all hiatuses;
- The instructors/evaluators will be instructed to be alert for the emergence of symptoms of angina and shortness of breath. Participants will be instructed to discontinue exercise if there is significant pain, weakness, or joint swelling after exercise.
- We will ensure that that the site has immediate access to a phone and that provision of interventions and evaluations are undertaken in the immediate vicinity of a phone. All trainers and evaluators will also be encouraged to carry cell phones;
- All activities will occur inside an air-conditioned facility because environmental extremes are poorly tolerated;
- Every precaution will be taken to provide fluids, rest and other measures to insure each participant is comfortable, safe and secure in the testing environment.

Confidentiality of data is maintained by using research identification numbers that uniquely identify each individual. Safeguards are established to ensure the security and privacy of participants' study records. The information collected from participants in this study has a low potential for abuse, since the data do not address sensitive issues. Nevertheless, appropriate measures are taken to prevent unauthorized use of study information. The research ID number is used. The research records are kept in a locked cabinet in the locked office of the PI. The files matching participants' names and demographic information with research ID numbers are kept in a separate locked room and are stored in a locked file that uses a different key from that of all other files. Only study personnel have access to these files. Electronic data will be stored in a password-protected file on a secure network. After the study is completed, procedures for long-term storage of VA data will be followed.

FMRI data will be stored in a secure electronic environment in a locked office (6205 A&B) at the Woodruff Memorial Research Building, [name], without identifiers.

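### No medical review is stated before training resumes after a new cardiac-type symptom that falls short of serious illness, on site or at home

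*Combined protocol and SAP*

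**What the plan says.** The rules on symptoms during training are in the bullet list under Protection Against Risk, in section 9 (DSMP).

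- Cardiac warning signs: "The instructors/evaluators will be instructed to be alert for the emergence of symptoms of angina and shortness of breath". No action is attached to this.
- Stopping, in the same bullet: "Participants will be instructed to discontinue exercise if there is significant pain, weakness, or joint swelling after exercise".
- Routine enquiry: "At each exercise session, participants will be questioned about the presence of musculoskeletal symptoms".
- Pause: "If adverse symptoms develop a 1-week hiatus from the exercise session will be enforced", with static stretching meanwhile. Then: "A slow reintroduction of the exercise program will follow all hiatuses".
- Clearance: "If a participant experiences a significant illness requiring mobility restriction, surgery or hospitalization, the project coordinator will contact the participant's primary physician for clearance". The sentence goes on to specify return to the intervention classes.
- General advice: "Written instructions highlighting some fundamental guidelines all study participants should do to ensure that they are exercising safely will be provided".

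Other sections matter here too. The opening of section 9 names exercise-induced cardiovascular events as a possibility and says the risk is kept down by enrolling people whom a health professional has cleared. Section 5 (Fitness Assessments) has the researcher end the fitness test if a participant reports feeling faint, dizzy or short of breath. Section 5 (Research Plan) provides CPR-certified monitoring of sessions and defibrillators at the site. The Research Design for Specific Aim 3 adds a 26-week exercise program with a bicycle supplied for home use.

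**The concern.** Participants are sedentary adults aged 60 to 89 whose training intensity is raised week by week. Entry clearance describes a person without new symptoms. If exertional chest pressure or unaccustomed breathlessness then appears, that clearance is in doubt, and the natural question is who decides whether the person may train again.

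The plan accepts this logic for serious illness, where the coordinator must go back to the primary physician. It does not state the same step for the cardiac symptoms it names itself. A participant with new chest pressure who is neither admitted to hospital nor restricted in mobility falls below the clearance trigger. What is at stake is participant safety, specifically a return to progressive exercise without a medical opinion on the new symptom.

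**Working it through.** No arithmetic applies: the point depends on no error rate, effect size or sample size, and the plan gives no figure to reproduce. The check is to follow one case through the text: a new angina-type symptom, or new shortness of breath, that does not lead to mobility restriction, surgery or hospitalization.

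**Step 1. Is it detected?** Staff are to be alert, but the question put at every session concerns musculoskeletal symptoms. Detection rests on observation or on the participant volunteering the symptom. At home, no on-site instructor is described.

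**Step 2. Does exercise stop?** Possibly. The stop instruction covers significant pain, which can include chest pain, and weakness. It does not name breathlessness, faintness or dizziness. The fitness test does name these three and ends when they are reported, so the test has a more explicit symptom rule than the training.

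**Step 3. What governs return?** This turns on whether *adverse symptoms* includes cardiac symptoms.

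| Reading of *adverse symptoms* | Stated route | Medical review stated? |
|---|---|---|
| Includes cardiac symptoms | 1-week hiatus, then slow reintroduction | No |
| Musculoskeletal and similar only | None stated | No |

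**Step 4. Does another provision supply the review?**

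| Provision | What it does | Covers fitness to resume after a lesser symptom? |
|---|---|---|
| Physician approval (sections 5, 6 and 9) | Required before starting | No; given before the symptom |
| Clearance and vital-sign limits for the fitness test (section 5) | Gate the test | No; tied to the test, and repetition of clearance is not stated |
| CPR-certified monitoring, defibrillators (section 5) | Deal with the acute event | No |
| Readiness questionnaire (Measures for Specific Aim 3) | Asks about difficulty with physical activity | No; neither timing nor a clearance action is given |
| Notice to the IRB within five days (section 8) | Reporting and oversight | No; it falls inside the 7-day hiatus but is not clinical clearance |
| Illness, surgery or hospitalization bullet (section 9) | Coordinator obtains clearance | No; its trigger is not met |

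**Step 5. The home phase.** The clearance bullet is worded for "primary physician for clearance to return to the intervention classes", and the other precautions presuppose a site with instructors and a nearby phone. The daily log in the Measures for Specific Aim 3 records exercise activity; no symptom entry is described. No symptom pathway is stated for the 26 weeks at home.

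On both readings, and in both settings, the review step is absent from the stated rules.

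**The case against.** The strongest reply is that the text does not order anyone back to exercise. A reader might infer that the plan sends a participant with angina back after one week without review. The documents do not support that. It requires the broad reading of *adverse symptoms*, whereas the bullet list is introduced as reducing exercise-related injuries, which gives the narrow reading some support. The sentence on slow reintroduction says how training restarts after any hiatus. It is compatible with prior clearance, and naturally also covers absences for illness, where clearance is required. So this is an unstated step, not a rule that bypasses review. That part of the objection stands.

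It is also fair to say that the plan has real safeguards: entry approval, supervised sessions on site, defibrillators, a stop instruction, a symptom rule in the fitness test, and prompt IRB notice. Staff may well refer in practice. The written safety instructions and the ACSM guidelines may say more, and the Additional measures for Specific Aim 3 point to testing guidelines under a Human Subjects Protection heading that is not in the available text. These points limit the claim to the rules as stated. They do not supply the missing step, because each safeguard that can be read deals with entry, the acute event, the test or reporting.

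**Conclusion.** The point holds as an omission in the stated rules: after a new cardiac-type symptom below the serious-illness threshold, no medical review is stated before training resumes, whether on site or in the 26-week home phase. Confidence in that is high, because it follows on either reading of *adverse symptoms* and no other section fills the gap. The more specific consequence, a return after one week without review, is conditional on the broad reading and should not be reported as fact.

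The plan gives no symptom rate, so the risk cannot be sized; counting training sessions would describe exposure, not risk. No endpoint or error rate is affected. The omission should be fixed because the plan itself relies on medical clearance to limit cardiovascular risk, and the remedy extends a route it already uses. The conclusion assumes that the instructions and guidelines not reproduced in the text do not already impose the review; if they do, the amendment only needs to say so.

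**What to change.** Amend Protection Against Risk as follows.

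1. Limit the 1-week hiatus and gradual restart to musculoskeletal and other non-cardiac symptoms.
2. For chest pain or pressure, faintness or dizziness, or shortness of breath that is unusual for the effort or does not settle with rest: stop exercise; start the emergency response if the symptom is ongoing or severe; and require primary-physician clearance, through the existing coordinator route, before any return on site or at home. Ordinary breathlessness that settles with rest does not trigger this. The breathlessness wording is a suggestion for the study's clinicians to settle, since the documents give no threshold.
3. Add these symptoms to the question asked at each session. For the home phase, add them to the daily log with an instruction to stop and call emergency services if symptoms are ongoing or severe, and otherwise the project coordinator. A log entry alone may be read too late.

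The cost is a wording amendment, a longer per-session question and an extra log line with its instruction. Some participants will miss sessions while waiting for clearance, and some referrals will prove unnecessary.
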